9.4.1.8 Unscheduled Safety Visit

If an SAE occurs in a subject, the subject will return to the site for a PK sample, as close as possible to SAE onset. Procedures and assessments are as follows:

1. Review concomitant medications.
2. A blood sample will be taken for PK analysis. The exact date and time of sampling must be documented.
3. Review the Drug Intake Diary for completion compliance and for the date and time of the last dose of study drug prior to the PK sample.
4. Perform physical and neurological examination and vital signs measurement (blood pressure, heart rate, respiration rate, weight and oral temperature). The neurological examination can be conducted \pm 1 day of the scheduled protocol visit. Complete TCNS in the course of the neurological examination, as well as NTSS-6 (with input from the caregiver) to ensure the subject did not develop new signs or symptoms of neuropathy.
5. Record AEs. AESIs (worsening of NFM [calculated as the average of the Screening visit and Baseline visit data] or prolongation of QTc) must be treated as SAEs and notified to ICON PV within 24 hours (see [Section 12.1.1](#)). ICON PV or ICON MM will then contact the study site to define follow-up activities and to assess whether the subject must be withdrawn from study.

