- Sensory - Sural nerve: In case the Sural nerve is not measurable for SNAP, the Ulnar nerve or Median nerve will be used for sensory neurography as “back-up” nerves. SNAP amplitude will be assessed Baseline-to-peak. The number of repetitions will be according to local standards. NCV will be calculated according to local standards.
- Motor - Peroneal nerve: Only if the Peroneal nerve is not measurable for CMAP, the Tibial nerve motor component will be used as back-up. CMAP amplitude will be measured peak-to-peak. The number of repetitions will be according to local standards. NCV will be calculated according to local standards.

The NFM should follow existing local standards and procedures and should be run in a consistent fashion. Please see [Table 4](#) for a summary of the NFM assessments and personnel involved:

Table 4 NFM Requirements

Outcome	Test	Conducted by	Frequency	Protocol reference
Clinician-rated	Toronto Clinical Neuropathy Score (TCNS)	Certified neurologist or a physician who has received appropriate training from a neurologist	Every visit, except ad hoc or unscheduled safety visits, i.e. maximum 6 times	Section 12.5
Sensory testing	Vibration detection threshold			Section 12.7
	Thermal detection			
Neurography	Motor and sensory nerve (amplitude and conduction velocity)	Individual trained in these techniques, which may include (but is not limited to) a neurologist, neurophysiologist or neurophysiology assistant		
Subject-rated	Neuropathy Total Symptom Score-6 (NTSS-6)	Health care professional, e.g. study nurse, study coordinator	Every visit, including ad hoc and unscheduled safety visits, i.e. approximately 6 times	Sections 12.7 and 12.8

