15.2.3.7 Evaluation of Safety Variables

Clinical safety laboratory data: clinical safety laboratory data will be presented by treatment group and overall. For each visit, the actual result and the change from Baseline will be presented. Count and shift tables for values outside the normal ranges will be presented as appropriate. In addition, individual listings will be provided for subjects with at least one value outside the normal range for a given laboratory parameter.

AEs: TEAEs will be described using descriptive statistics, and coded according to the Medical Dictionary for Regulatory Activities (MedDRA) system organ class and MedDRA preferred term, by treatment group and overall for the following categories:

- All TEAEs
- Treatment-emergent AESI
- Treatment-emergent SAEs

- TEAEs by severity
- Drug-related TEAEs
- TEAEs leading to temporary or permanent discontinuation of study drug
- TEAEs leading to study discontinuation

ECG: The results for the ECG will be presented by treatment group and overall. For each visit, the actual results and the change from Baseline will be presented.

CSSRS: Suicidal ideation, suicidal behaviour and self-injurious behaviour without suicidal intent, as well as suicide-related TEAEs based on the CSSRS during treatment, will be tabulated by treatment group and overall. Shift tables by treatment group will be prepared for changes in CSSRS categories from Baseline to during treatment, as well as for the maximum suicidal ideation score. In addition, individual listings will be provided for subjects with at least one occurrence of suicidal ideation, suicidal behaviour or self-injurious behaviour without suicidal intent at any time under treatment.

Vital signs: The results for vital signs will be presented by treatment group and overall. For each visit, the actual results and the change from Baseline will be presented.

Physical examination: Abnormal results will be presented by individual listings.

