All data will be presented on listings in order of treatment group, subject, site [wherever defined], assessment date/time and assessment (in order collected on eCRF, unless specified otherwise). Dates will be presented in the format DDMMYY. Times will be displayed in 24-hour clock format. Numbering of tables, figures and listings will follow ICH E3 guidelines.

Unless noted otherwise, unscheduled measurements will be excluded from the descriptive statistical analysis. However, unscheduled measurements that were performed immediately after the scheduled measurement, in case of a previous measurement error (e.g. equipment failure), will not be excluded from the analysis. In these cases, the original erroneous measurement will be excluded from the analysis and the unscheduled visit substituted. All the unscheduled measurements will be included in the listing.

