7.8.2 Clinical Safety Laboratory Parameters

Descriptive statistics for absolute value and absolute change from Baseline [only for continuous results parameters, otherwise display percentage change from Baseline] for protocol specified laboratory parameters of biochemistry, haematology and urinalysis will be presented for Baseline (Week 0) to EOT (Week 12) by treatment group and overall. International System of Units (SI units) will be used for the analysis. The abnormality in laboratory parameters will be summarized by treatment group.

Values outside the normal range (N) will be categorized as H (above the normal range) or L (below the normal range) based on the reference range of the Safety Laboratories. Shift tables will be presented showing the number of subjects per treatment group with N, H or L at the Baseline (Week 0) to EOT (Week 12). Laboratory test results will be listed by including laboratory blood tests, which are to only be performed at screening and abnormal values outside normal ranges will be flagged.

The following laboratory test parameters will be summarized:

Laboratory Test	Parameters
Haematology	Haemoglobin, Haematocrit, Platelet count, Red blood cell count, White blood cell count and differential, Basophils, Eosinophils, Monocytes, Neutrophils and Lymphocytes
Biochemistry	Alkaline Phosphatase, Alanine Aminotransferase (ALT), Aspartate Aminotransferase (AST), Gamma-glutamyl transpeptidase, Phosphorous, Potassium, Uric acid, Bilirubin (total), Protein (total), Creatinine, Follicle-stimulating hormone [Females only. To be taken only if there is clinical concern about the subject's menopausal status], Human chorionic gonadotrophin [Pregnancy test on women of childbearing potential only]
Urinalysis	Urate crystals, phosphate crystals, bilirubin crystals, blood, clarity, colour, glucose, ketones, leukocytes, protein, squamous epithelial cells, trans. epithelial cells, triple phosphate crystals, Microscopic examination [Performed only if required, based on urinalysis results]

Metabolic indicators	Glucose, fasting, Cholesterol, Triglycerides, High-density lipoprotein-cholesterol, Low-density lipoprotein-cholesterol, HbA1c, Very Low-density lipoprotein (VLDL) Cholesterol
----------------------	---

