7.8.4.1 Neuropathy Total Symptom Score (NTSS)-6

The six questions of NTSS-6 should be completed as part of the assessment of subjects’ medical history; also asking for input from the caregiver to make sure no information is lost. Each item will also be graded for its frequency and intensity, adding up to a total score from ‘0’ to ‘21.96’ points (maximum score per symptom is 3.66). A total score of > 6 would exclude the subject from the study.

Descriptive statistics for absolute value and absolute change from Baseline for total NTSS-6 score and each score per symptom will be presented for screening, Baseline (Week 0), Interim (Week 4), Interim (Week 8) EOT (Week 12) and Follow-up (4 weeks post last dose of study drug) visits by treatment group and overall. The subjects with total NTSS-6 score > 6 will also be summarized by treatment group and overall for screening, Baseline (Week 0), Interim (Week 4), Interim (Week 8) EOT (Week 12) and Follow-up (4 weeks post last dose of study drug) visits. NTSS-6 data will be listed.

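### Unscheduled laboratory, ECG, vital-sign and neuropathy readings reach only the listings, and no such table counts subjects by worst value after first dose

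*SAP*

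**What the plan says.** SAP 5.1 sets a default for all summaries: "unscheduled measurements will be excluded from the descriptive statistical analysis". There is one exception: "unscheduled measurements that were performed immediately after the scheduled measurement, in case of a previous measurement error (e.g. equipment failure), will not be excluded"; the repeat then replaces the faulty value. For everything else, "All the unscheduled measurements will be included in the listing".

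The safety sections do not lift the default. SAP 7.8.3 (ECG) and 7.8.6 (vital signs) refer to scheduled visits. For NTSS-6, SAP 7.8.4.1 says "The subjects with total NTSS-6 score > 6 will also be summarized by treatment group and overall for screening" and then names Baseline, Weeks 4, 8 and 12 and Follow-up. SAP 7.8.4.2 names the same six visits for abnormal TCNS sensory tests.

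For laboratory data, SAP 7.8.2 plans shift tables of subjects per treatment group "with N, H or L at the Baseline (Week 0) to EOT (Week 12". Protocol 15.2.3.7 says of the same data: "For each visit, the actual result and the change from Baseline will be presented", and adds count and shift tables for out-of-range values.

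For nerve function, protocol 15.2.3.7 plans count tables, by group and overall, of subjects with NTSS-6 above 6 and of subjects with an abnormal TCNS sensory test. It also asks for particular attention to change within subjects over the study. SAP section 10 declares no change from the protocol's methods.

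**The concern.** Many off-schedule readings in this trial are taken because something has happened. NTSS-6 is completed at ad hoc calls, which subjects may make to report an AE. NTSS-6, TCNS and vital signs are taken when a subject returns after an SAE. Laboratory tests are added when judged clinically appropriate, and an ECG considered clinically significant is repeated. These are the readings that the default rule removes from the by-arm tables.

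Peripheral nerve effects are a named safety concern, and SAP 7.8.4 gives detection of worsening within a subject as the aim of nerve function monitoring. That question is per subject: did this person cross the threshold at any time on drug? The tables as specified answer a per-visit question from scheduled readings only. A subject whose only NTSS-6 score above 6 came at an unscheduled contact would be visible in a listing but absent from the comparison between arms.

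**Working it through.** **Step 1. Where each off-schedule reading goes.**

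| Reading | Protocol source | SAP summary | By-arm table? |
|---|---|---|---|
| NTSS-6 at an ad hoc call | 9.4.1.5, Table 1 | 7.8.4.1, six named visits | No, listing only |
| NTSS-6 and TCNS at the SAE-triggered visit | 9.4.1.8, Table 1 examination row | 7.8.4.1 and 7.8.4.2, six named visits | No, listing only |
| Vital signs at that visit | 9.4.1.8 | 7.8.6, scheduled visits | Only if reported as an AE |
| Extra laboratory tests | 12.2 | 7.8.2 with the 5.1 default | Only if reported as an AE |
| Repeat ECG | 12.3 | 7.8.3, scheduled visits | Only if it corrects a measurement error or is reported as an AE or AESI |

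The AE route is conditional. Protocol 12.1.1.2 makes a laboratory, vital-sign or ECG abnormality an AE only if a listed criterion is met, and one criterion is the investigator's judgement. For nerve function, protocol 12.1.1 limits the AESI to worsening that qualifies as a potential safety signal. Section 12.7.1 requires at least two related parameters and no other plausible explanation for that. An isolated NTSS-6 score above 6 need not qualify.

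**Step 2. By-visit counts do not give subjects ever affected.** There are four scheduled post-Baseline visits with NTSS-6 and TCNS: Weeks 4, 8, 12 and Follow-up. One subject above 6 at all four, and four subjects above 6 at one visit each, produce the same row of counts. The number of subjects ever above 6 cannot be recovered from the table even for scheduled readings.

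**Step 3. Visits in the laboratory shift.** Table 1 schedules post-Baseline safety samples at Weeks 4, 8, 12 and Follow-up, so four.

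- Read as two end points, the shift uses Week 12 only: 1 of 4.
- Read as a span, it uses Weeks 4, 8 and 12: 3 of 4.
- Follow-up is excluded on both readings.

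The ECG shift in SAP 7.8.3 refers to all post-dose scheduled visits, so clearer wording was available. To show what the choice could mean, assume independent excursions with probability 5% at each of Weeks 4, 8 and 12. The share of subjects with at least one is 1 − 0.95³ = 14.3%, against 5.0% at Week 12 alone. In 87 subjects that is 12.4 against 4.4. The 5% and the independence are assumptions.

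**Step 4. The protocol's own detection figure.** Section 15.1 gives the chance of seeing an untoward nerve effect in at least one of 78 subjects as about 90% at a true rate of 3%, and above 98% at 5%. The formula is 1 − (1 − p)^78:

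- p = 0.03: 1 − 0.97^78 = 90.7%
- p = 0.05: 1 − 0.95^78 = 98.2%

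Both reproduce. The quantity is per subject and has no visit attached. If a share f of affected subjects is seen only in readings the tables omit, the chance that a table shows at least one is 1 − (1 − p(1 − f))^78:

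| f (assumed) | p = 3% | p = 5% |
|---|---|---|
| 0 | 90.7% | 98.2% |
| 0.10 | 88.2% | 97.2% |
| 0.25 | 83.1% | 94.9% |
| 0.50 | 69.2% | 86.1% |

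The documents give no value of f, so this shows sensitivity and is not an estimate.

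**The case against.** The strongest reply is that the events behind these readings are already counted. Ad hoc calls can be made to report an AE and the unscheduled visit follows an SAE, and both enter the incidence tables in SAP 7.8.1. QTc above 480 msec or a rise above 60 msec is an AESI under protocol 12.1.1 and has its own table. CSSRS endpoints are already defined over the whole treatment period. All of this stands, and it rules out several stronger readings.

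- A reader might infer that the safety counts as a whole miss these subjects. They do not: AE, SAE, AESI and CSSRS tables do not depend on scheduled readings.
- A reader might cite a subject whose liver enzymes rose and recovered after stopping drug. Protocol 12.1.1.2 makes an abnormality that leads to stopping or interrupting treatment an AE, and SAP 7.8.1 tabulates it by arm.
- A reader might infer that excursions resolving before Week 12 vanish generally. NTSS-6 and TCNS counts and ECG shifts include the interim scheduled visits. The point can apply only to the laboratory shift, and only on the end-point reading. SAP 7.8.2 uses the same phrase for its descriptive statistics, SAP 5.1 makes by-visit summaries the default, and 7.8.2 adds an abnormality summary with no visit limit. The span reading is therefore open.
- A reader might call the tables biased towards no signal. Where a repeat follows an abnormal scheduled value, that value stays in the table. Only subjects whose sole abnormal reading is off schedule are lost.
- A reader might size the loss by assuming that 20-40% of crossings occur only off schedule. That returns the assumption as the result.

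It is also fair to say that protocol 15.2.3.7 does not state that its subject counts are over all times, so by-visit counts are not a plain breach. But they do not serve the within-subject purpose stated there, and the AE route does not cover readings that miss its criteria.

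**Conclusion.** The point holds in a limited form. As written, off-schedule NTSS-6 and TCNS readings, and unscheduled laboratory, ECG and vital-sign values outside the AE and AESI criteria, are shown only in listings. No laboratory, ECG, NTSS-6 or TCNS table is defined by worst value after first dose. The laboratory shift is ambiguous between 1 and 3 of 4 post-Baseline samples and omits Follow-up either way, while the protocol says each visit. If only Week 12 is meant, the SAP narrows the protocol without recording it in section 10.

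The direction for measurement-based subject counts is clear: leaving readings out can lower the number of subjects ever above a threshold and cannot raise it. The size cannot be derived from the documents, and the illustrations rest on assumed rates. Nothing here affects the efficacy analysis or the AE-based safety tables. It is a low-cost improvement to what the safety tables can show.

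**What to change.** Keep the by-visit summaries on scheduled readings. In SAP 7.8.2 to 7.8.4 add tables, by arm and overall, of the worst value at any time after first dose, with unscheduled readings included:

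- laboratory shift from Baseline to highest and from Baseline to lowest value;
- subjects with NTSS-6 above 6;
- subjects with any abnormal TCNS sensory test;
- QTcF against the protocol's own 480 msec and 60 msec thresholds.

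Add one sentence to SAP 5.1 exempting these tables from the exclusion. State in SAP 7.8.2 that laboratory shifts cover Weeks 4, 8, 12 and Follow-up.

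The cost is a few extra tables from existing data, with no new assessments.

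Separately, the protocol contradicts itself on TCNS at unscheduled safety visits. Section 9.4.1.8 says "Complete TCNS in the course of the neurological examination, as well as NTSS-6 (with input from the caregiver", and the examination row of Table 1 agrees. Table 4 gives the TCNS frequency as "Every visit, except ad hoc or unscheduled safety visits, i.e. maximum 6 times", and the nerve function row of Table 1 marks nothing at that visit. This concerns data collection and does not bear on the SAP rule, but the passages must be reconciled so that it is clear which TCNS readings exist.

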5.2 Specification of Baseline Values

For efficacy variables: Baseline value is defined as the latest Week 0 observation prior to or on the date of the first dose of study drug. The exception is MMSE which is defined as the latest Screening or Week 0 observation prior to or on the date of the first dose of study drug. When MMSE results are analysed as part of the ADCOMs analysis, use of screening results are not allowed, in order to ensure that all Baseline values contributing to the ADCOMs refer to the same point in time. For safety endpoints: Baseline value is defined as the observation prior to or on the date of the first dose of study drug.

5.3 Multiple Comparisons and Multiplicity

Multiplicity between both primary endpoints will be handled using an a priori hierarchical approach.

6.0 ANALYSIS POPULATION

The populations used for analysis will include Full Analysis Set (FAS), Per Protocol (PP) Analysis Set, Safety Analysis Set, PK Set and PD Set. The success of the primary efficacy endpoints will be evaluated based on the FAS; these primary efficacy endpoints will also be analyzed for the PP analysis set. The evaluation of secondary efficacy endpoints will be based on FAS and PP analysis set. The evaluation of safety endpoints will be based on safety analysis set. PK set and PD set will be used for PK and PD endpoints analysis.

6.1 Full Analysis Set (FAS)

The FAS will consist of all subjects randomised who received at least one dose of study drug. Subjects will be analysed in the treatment group they were randomised to even if they received incorrect study drug. Where changes from Baseline are analysed, subjects will be included only if both a Baseline and at least one valid post-Baseline measurement are available.

The FAS will be the primary analysis set for efficacy analyses.

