5.0 STATISTICAL CONSIDERATIONS

5.1 General Considerations

Statistical analyses will be performed using SAS software, version 9.3 or higher. Formal hypothesis will be tested in this study and it will be explained in detail on following section.

Continuous data will be summarized using number (n), mean, standard deviation (SD), minimum value, median, maximum value and, if appropriate, number of missing values. Unless noted otherwise, summaries will be produced by visit (where applicable) and results will be presented overall and by treatment group. If more than one value is reported at a scheduled visit, the value collected closest to the intended visit date will be used. In the case of a tie, the latest version will be summarized. If there is more than one value reported at the same date, the average value of multiple values will be obtained. Where changes from Baseline are analysed, subjects will be included only if both a Baseline and at least one valid post-Baseline measurement are available.

Categorical data will be summarized using number (n) and percentages. Percentages will be calculated based on the number of non-missing values (if result display by visit) otherwise it will be calculated based on the population count. The number of missing values will be presented as a separate category with no percentage, if one or more subjects have missing data for the summary. Otherwise, all categories will be presented (even if no subjects are counted in the category). Counts of zero in any category will be presented without percentage.

Precision of summary statistics:

- Integer – Sample size (n, N) and number of missing responses (if displayed).
- One additional decimal place than reported/collected on the electronic Case Report Form (eCRF) – mean and median
- Two additional decimal places than reported/collected on the eCRF – standard deviation.
- Same number of decimal places as reported/collected on the eCRF – minimum, maximum.
- Percentages, CV – one decimal place.
- P-values will be presented for three decimal points (i.e., 0.xxx).

Precision of output display:

- Report output will be generated using SAS (version 9.3 or higher) ODS RTF with no borders or framing around table elements.
- Font – Courier New font with minimum of eight point font size
- Margins – For USA, minimum of 3/4” bound edge margin and 3/8” other margins on 8.5”x11” paper.

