7.7 Efficacy Endpoints and Analyses

The primary efficacy analysis will be based on both FAS and PP population. Sensitivity analyses with primary efficacy endpoints will be based on FAS population. The secondary efficacy analysis will be analysed in a descriptive summary statistics based on FAS and PP population. Descriptive summary statistics mentioned in section 5.1 will be performed for all data used

within the context of the efficacy analysis models. Summaries will be presented by visit and by treatment group. Comprehensive listings of all data will be presented.

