Whilst the European Medicines Agency discussion paper⁵ foresees the use of the linear models for sensitivity analyses, complementing different methods of primary analyses, the type and order of analyses in this study – ANCOVA as primary efficacy analysis and placebo-based imputation as sensitivity analysis – are chosen in a different fashion due to the following reasons:

- The development stage this study is associated with, where the primary aim is to explore a possible therapeutic effect of Xanamem™; in conjunction with
- The relatively short study duration, which can be expected to reduce the number of missing values in either treatment group and
- The fact that the primary efficacy variables will only be assessed at Baseline (Week 0) and Week 12/EOT.

Sensitivity analyses aim at assessing the robustness of the primary efficacy analysis. The following four analyses will be performed:

1) An additional ANCOVA, imputing missing Week 12/EOT data based on resampling from the placebo subjects, taking Baseline values into account

Process

- a) Select records from placebo group with non-missing ADCOMs score at Week 12
- b) Select records from Xanamem group with missing ADCOMs score at Week 12

- c) Merge datasets from a) and b)
(Total number of records in merged dataset = number of records in dataset a) * number of records in dataset b))
- d) Using Baseline (placebo) and Baseline (Xanamem), calculate DIFF variable to find record in placebo group which has smallest in difference with Baseline in test group
DIFF = abs (Baseline (Xanamem) – Baseline (placebo))
- e) Calculate RANDNO variable with RANUNI function and select the smallest randno
- f) Select 1 record for each missing case in Xanamem group and impute ADCOMs score at Week 12 based on ADCOMs score at Week 12 in placebo group
- g) Calculate change from Baseline based on imputed ADCOMs score at Week 12 for Xanamem group
- h) Repeat a) to g) for placebo group and combine both datasets with the records from both groups with non-missing ADCOMs score at Week 12.
- i) Run proc ANCOVA specified above

The following SAS statements will be employed:

For Xanamem group:

```

data placebo;
set indata;
if <treatment group> = Placebo and <VISIT> = Week 12 and AVAL <> missing;
rename CHG=CHG_P BASE=BASE_P ID=ID_P AVAL=AVAL_P;
run;

```

```

data test;
set indata;
if <treatment group> = Test and <VISIT> = Week 12 and AVAL = missing;
run;

```

```

proc sql;
create table outdata as
select *from test, placebo ;

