quit;

```

```
proc sort data=outdata;  
by id id_p;  
run;
```

```
data outdata1;  
set outdata;  
diff=abs(BASE - BASE_P);  
seed_no=ID * ID_P;  
randno=ranuni(seed_no);  
AVAL = AVAL_P;  
CHG=AVAL - BASE;  
run;
```

```
proc sort data=outdata1 out=outdata2;  
by id diff randno;  
run;
```

```
proc sort data=outdata2 nodupkey;  
by id;  
run;
```

```
data outdata3;  
set outdata2;  
keep ID <treatment group> BASE AVAL CHG;  
run;
```

For placebo group, follow above process and keep the imputed data in *outdata4*.

```
data nomissing;  
set indata;  
if aval ^=missing;  
run;
```

```
data FINAL;  
set outdata3 outdata4 nomissing;  
run;
```

where CHG= Change ADCOMs score from Baseline, BASE=baseline ADCOMs score and AVAL=ADCOMs score at Week 12/EOT.

Run PROC MIXED procedure specified above with FINAL dataset.

2) An additional ANCOVA, adding site as a factor. Sites will be pooled by country if randomized subjects will be less than or equal to 10. The following SAS statements will be employed:

```
proc mixed data=xxxx ;  
    class <treatment group> <site>;  
    model < change ADCOMs score> = <baseline ADCOMs score>  
    <treatment group> <site>;  
    lsmeans <treatment group>/ diff cl alpha=0.05;  
ods output lsmean=xxx diffs=xxx;  
run;
```

3) An additional ANCOVA, imputing missing Week 12/EOT data based on placebo-based multiple imputation with missing not at random (MNAR) assumption.

Process

Missing data at Week 12/EOT will be imputed using a regression model based on placebo-based imputation model. The imputation model will include the Baseline values and Week 12/EOT values. The imputation model for the missing observations in both the Xanamem group and the placebo group will be constructed from the observed data in the placebo group only. Under this approach we assume that patients with missing data in both treatment groups would have outcomes like a patient in the placebo group as soon they become missing. The imputation will be performed for 100 times and imputed datasets will be analysed using an ANCOVA model. Approximately 100 imputed datasets will be created and results from the analysis of each imputed dataset will be combined using Rubin's method.

- The following SAS statements will be employed:

```

proc mi data=xxxx nimpute=100 seed=3489876 out=yyyy;
class < treatment group>;
monotone reg (<ADCOMs score at week 12/EOT>);
mnar model(<ADCOMs score at week 12/EOT> /modelobs=(<treatment
group>='Placebo'));

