var <baseline ADCOMs score> < ADCOMs score at week 12/EOT>;
run;

data zzzz;
set yyyy;
<change ADCOMs score> = <ADCOMs score at week 12/EOT> -< baseline
ADCOMs score>;
run;

* For 95% Confidence Interval;
proc mixed data=zzzz;
by _imputation_;
class <treatment group>;
model <change ADCOMs score>=<baseline ADCOMs score> <treatment
group>;
lsmeans <treatment group>/ diff cl alpha=0.05;
ods output lsmeans=aaaa diffs=bbbb;
run;

** LSmeans;
proc mianalyze parms(classvar=full)=aaaa;
class <treatment group>;
modeleffects <treatment group>;
ods output parameterestimates=cccc;
run;

** Differences;

```

```

proc mianalyze parms(classvar=full)=bbbb;
class <treatment group>;
modeleffects <treatment group>;
ods output parameterestimates=dddd;
run;

* For 90% Confidence Interval;
proc mixed data=zzzz;
by _imputation_;
class <treatment group>;
model <change ADCOMs score>=<baseline ADCOMs score> <treatment
group>;
lsmeans <treatment group>/ diff cl alpha=0.10;
ods output lsmeans=aaaa2 diffs=bbbb2;
run;

** Differences;
proc mianalyze parms(classvar=full)=bbbb2;
class <treatment group>;
modeleffects <treatment group>;
ods output parameterestimates=dddd2;
run;

```

The analysis described above will be repeated for ADAS-Cog v14.

4) An additional ANCOVA, imputing missing Week 12/EOT data based on multiple imputation using both the Xanamem and placebo group with the missing at random (MAR) assumption.

Process

Missing data at Week 12/EOT will be imputed using a regression based imputation model. The imputation model will include Treatment Group, Baseline values and Week 12/EOT values. The imputation model for the missing observations in both the Xanamem group and the placebo group will be constructed from the complete-case observed data for patients in both the Xanamem group and the placebo group. Under this approach we assume that patients with

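### The FAS inclusion rule for change-from-Baseline analyses conflicts with sensitivity analyses 1, 3 and 4, which must impute the subjects that the rule leaves out

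*SAP*

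**What the plan says.** Membership of the full analysis set is broad. SAP 6.1: "The FAS will consist of all subjects randomised who received at least one dose of study drug". The same section then narrows it for each analysis: "Where changes from Baseline are analysed, subjects will be included only if both a Baseline and at least one valid post-Baseline measurement are available". SAP 5.1 repeats the restriction ("subjects will be included only if both a Baseline and at least one valid post-Baseline measurement are available"), and so do protocol 15.2.1 and the protocol synopsis.

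SAP 7.7 fixes the population for the robustness checks: "Sensitivity analyses with primary efficacy endpoints will be based on FAS population". SAP 7.7.1.1 gives the assessment schedule as one reason for its choice of methods: "The fact that the primary efficacy variables will only be assessed at Baseline (Week 0) and Week 12/EOT".

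Three of the four sensitivity analyses in SAP 7.7.1.1 impute:

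- Analysis 1, resampling from placebo subjects matched on Baseline: "Select records from Xanamem group with missing ADCOMs score at Week 12", then the same steps for placebo.
- Analysis 3, placebo-based multiple imputation: "Missing data at Week 12/EOT will be imputed using a regression model based on placebo-based imputation model".
- Analysis 4, multiple imputation under missing at random: "Missing data at Week 12/EOT will be imputed using a regression based imputation model".

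Each ends in an ANCOVA on change from Baseline. Analysis 2 adds site as a factor and imputes nothing.

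**The concern.** The primary ANCOVA uses observed cases only. Analyses 1 and 3 are the only planned checks that depart from missing at random. A subject enters the imputation step because the Week 12/EOT score is missing. With one post-Baseline assessment, that same gap means the subject has no valid post-Baseline score and fails the inclusion rule.

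A programmer who builds the analysis data set from SAP 6.1 would pass only completers to the imputation code. The output would agree with the primary result because nothing had been imputed, and that agreement could be mistaken for robustness to drop-out. A programmer who starts from 7.7.1.1 would impute. The SAP does not say which instruction governs, so the population of the missing-data checks is not clearly prespecified.

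**Working it through.** **The plan's own numbers.** Protocol 15.1 gives a difference of 2 points, SD 5, one-sided alpha 0.05, power 80% and about 10% drop-out.

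- Per arm: n = 2 × (1.645 + 0.842)² × 5² / 2² = 77.3, rounded up to 78. Power at 78 per arm is 80.3%.
- Inflated for drop-out: 78 / 0.90 = 86.7, rounded up to 87 per arm, so 174 randomised and 156 planned completers.

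Both figures reproduce the protocol. Planned drop-outs are 174 − 156 = 18, or 18 / 174 = 10.3%, about 9 per arm.

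**Who passes each rule**, taking every planned drop-out to lack a Week 12/EOT score:

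| Instruction followed | Analysed | Imputed |
|---|---|---|
| Inclusion rule (SAP 5.1, 6.1) | 156 | 0 |
| Imputation steps (SAP 7.7.1.1) | 174 | 18 |

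The documents give a drop-out rate but no rate of missing EOT scores. Assumed missing rates of 5%, 10%, 15% and 20% of 174 give about 9, 17, 26 and 35 subjects to impute if the steps are followed. On the strict reading of the rule the count is 0 at every rate.

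**Effect on the results if the rule is applied.** In analysis 1 the sets to be imputed are empty, so the final data set is the observed records. In analyses 3 and 4 all 100 data sets are identical. The between-imputation variance B is then 0, and Rubin's total variance W + (1 + 1/100)B equals W, the ordinary ANCOVA variance. All three return the primary estimate and standard error.

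**Illustration.** One data set was simulated with 87 per arm, a true difference of −2, residual SD 5, and 9 Week 12 scores per arm removed at random. The Baseline mean of 25 and SD of 8 are assumptions.

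| Analysis | n | Imputed | Difference | SE |
|---|---|---|---|---|
| Primary ANCOVA | 156 | 0 | −1.785 | 0.769 |
| Analysis 1, inclusion rule applied first | 156 | 0 | −1.785 | 0.769 |
| Analysis 1, all dosed subjects | 174 | 18 | −2.040 | 0.710 |

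This shows the mechanism only. The size and direction of the change in a single run carry no information about the trial.

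**Whether any sentence resolves the conflict:**

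- SAP 5.1 has a general qualifier, but it opens the sentence on summaries by visit and treatment group, not the inclusion sentence.
- SAP 7.7.1.1 introduces its ANCOVA characteristics as defaults that may be overridden. That softens the observed-case condition listed there but does not amend 5.1 or 6.1.
- SAP 8.0 exempts the sensitivity analyses from the general bar on imputing values. It does not say which subjects enter.
- The printed code has placeholder input data sets, so it does not fix the population.

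None of these lifts the rule. Protocol 15.2.1 and 15.2.3.5 carry the same conflict for the resampling analysis.

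**The case against.** The strongest reply is that specific text prevails over general text. Subjects without a Week 12 score are FAS members by the first sentence of 6.1. Analysis 1 expressly selects them, imputes them in both arms and stacks them with the observed records. Analyses 3 and 4 describe imputation in both groups, and no printed code filters on a post-Baseline value. This stands as evidence of intent. A reader might infer from 6.1 that these analyses have nobody left to impute and must, run as written, return the complete-case result. The documents do not support that: it happens only if the 6.1 rule is applied upstream, against the written steps. An empty imputation set might also be noticed during programming.

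Two further points stand on size. First, 18 is planned drop-out, not expected missing EOT scores. Early terminators are asked to complete the EOT assessments where possible (footnote 2 to protocol Table 1, and sections 9.4.1.6 and 9.5), so some would have a score. Second, zero is not strict in every case. SAP Appendix 2 sets EOT (Week 12) at Day 81 to 89. If an earlier termination score is not mapped to Week 12, that subject passes the inclusion rule, counts as missing at Week 12 and could be imputed. The SAP does not settle the mapping.

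One could also read the rule as satisfied by a post-Baseline measurement of any kind. That is strained for an analysis of change in a particular score, and it would still drop subjects who leave before any post-dose assessment.

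**Conclusion.** The contradiction is real and of moderate importance; it is not a must-fix. A rule stated without exception in SAP 5.1, SAP 6.1, protocol 15.2.1 and the synopsis excludes essentially the subjects whom analyses 1, 3 and 4 are told to impute. The number imputed is essentially 0 under one instruction and up to about 18 of 174 under the other. The upper figure assumes the planned drop-out and that no early terminator supplies an EOT score. The lower figure assumes that a valid post-Baseline measurement means a Week 12/EOT score of the endpoint.

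The primary analysis, the type I error rate, the sample size and sensitivity analysis 2 do not depend on the answer. What depends on it is whether the planned missing-data checks test anything. The imputation steps show that the SAP means to include these subjects, so this is a drafting conflict and not a failure of design.

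**What to change.** Before unblinding:

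1. In SAP 5.1 and 6.1, limit the post-Baseline requirement to observed-case analyses.
2. In SAP 7.7, state that sensitivity analyses 1, 3 and 4 include all randomised, dosed subjects with a Week 0 value of the endpoint, whether or not a Week 12/EOT value exists.
3. State whether an early-termination score outside Day 81 to 89 counts as Week 12/EOT or as missing.
4. Report the number of subjects imputed per arm beside each of the three analyses, so that an empty imputation set would be visible.
5. Record the departure from protocol 15.2.1 in SAP 10.0, which at present declares no changes from the protocol.

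The cost is a few sentences and one extra row in the output tables. No new data are needed, and the sample size does not change.
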